**Visit 4 Week 24 (Day 168 ±7Days)**

The following procedures will be performed:

- Review ongoing concomitant medications
- Complete physical examination
- Neurological examination
- Weight
- Vital signs measured with the subject in a supine/semi-supine position (for at least 5 minutes prior), including blood pressure, pulse rate, pulse oximetry and temperature
- Standard 12-lead ECG (subject should be in a supine/semi-supine position for at least 5 minutes prior to assessment)
- Fasting blood samples for routine clinical labs (clinical chemistry, haematology). See table 2 for lab assessments
- Urine samples for urinalysis
- Urine pregnancy test only in women of childbearing potential
- Plasma vitamin B6 levels, and, if necessary, vitamin B6 supplements (pyridoxine (100 mg/day)) will be prescribed

- ALS evaluation procedures: ALSFRS-R, Slow Vital Capacity (SVC), Hand-Held Dynamometry, ALSAQ-40, Edinburgh Cognitive and Behavioural ALS Screen (ECAS), EQ-5D-5L, VAS, King's staging system and MiToS
- Blood sampling for biomarker: neurofilament light (NFL) Creatinine and creatine kinase will be measured in routine biochemistry lab testing.
- Urine collection for biomarkers: urinary extracellular domain of neurotrophin receptor p75 (Urinary P75ECD) and oxidative stress biomarker 8-hydroxyguanosine (8-OHdG)
- Blood sampling for RNA and serum collection for FBR (if consented)
- Cerebrospinal fluid (CSF) sampling for Future Biomedical Research (if consented)
- Nerve Conduction Study (NCS)
- Adverse Events monitoring
- Cost questionnaire
- Dispensing study medication
- Compliance check

#### **Visit 5 Week 36 (Day 252 ±7Days)**

The following procedures will be performed:

- Review ongoing concomitant medications
- Neurological examination
- Vital signs measured with the subject in a supine/semi-supine position (for at least 5 minutes prior), including blood pressure, pulse rate, pulse oximetry and temperature
- Fasting blood samples for routine clinical labs (clinical chemistry, haematology). See table 2 for lab assessments
- Urine samples for urinalysis
- Urine pregnancy test only in women of childbearing potential

- Plasma vitamin B6 levels, and, if necessary, vitamin B6 supplements (pyridoxine (100 mg/day)) will be prescribed.
- ALS evaluation procedures: ALSFRS-R, Slow Vital Capacity (SVC), Hand-Held Dynamometry, King's staging system and MiToS, EQ-5D-5L and VAS.
- Blood sampling for biomarker: neurofilament light (NFL). Creatinine and creatine kinase will be measured in routine biochemistry lab testing.
- Urine collection for biomarkers: urinary extracellular domain of neurotrophin receptor p75 (Urinary P75ECD) and oxidative stress biomarker 8-hydroxyguanosine (8-OHdG)
- Blood sampling for RNA and serum collection for FBR (if consented)
- Nerve Conduction Study (NCS) (if required)
- Adverse Events monitoring
- Cost questionnaire
- Dispensing study medication
- Compliance check

#### **Visit 6 Week 48 (Day 336 ±7Days)-End of Trial**

The following procedures will be performed:

- Review ongoing concomitant medications
- Complete physical examination
- Neurological examination
- Weight
- Vital signs measured with the subject in a supine/semi-supine position (for at least 5 minutes prior), including blood pressure, pulse rate, pulse oximetry and temperature
- Standard 12-lead ECG (subject should be in a supine/semi-supine position for at least 5 minutes prior to assessment)
- Fasting blood samples for routine clinical labs (clinical chemistry, haematology). See table 2 for lab assessments
- Urine samples for urinalysis

- Urine pregnancy test only in women of childbearing potential
- Plasma vitamin B6 levels, and, if necessary, vitamin B6 supplements (pyridoxine (100 mg/day)) will be prescribed.
- ALS evaluation procedures: ALSFRS-R, Slow Vital Capacity (SVC), Hand-Held Dynamometry, ALSAQ-40, Edinburgh Cognitive and Behavioural ALS Screen (ECAS), EQ-5D-5L, VAS, King's staging system and MiToS
- Blood sampling for biomarker: neurofilament light (NFL). Creatinine and creatine kinase will be measured in routine biochemistry lab testing.
- Urine collection for biomarkers: urinary extracellular domain of neurotrophin receptor p75 (Urinary P75ECO) and oxidative stress biomarker 8-hydroxyguanosine (8-OHdG)
- Blood sampling for RNA and serum collection for FBR (if consented)
- Blood sampling for FAB122
- Nerve Conduction Study (NCS) (if required)
- Adverse Events monitoring
- Cost questionnaire
- Dispensing study medication
- Compliance check

#### **Visit 7 Week 60 (Day 420 ±7Days)**

The following procedures will be performed:

- Review ongoing concomitant medications
- Neurological examination
- Vital signs measured with the subject in a supine/semi-supine position (for at least 5 minutes prior), including blood pressure, pulse rate, pulse oximetry and temperature
- Fasting blood samples for routine clinical labs (clinical chemistry, haematology). See table 2 for lab assessments
- Urine samples for urinalysis

- Urine pregnancy test only in women of childbearing potential
- Plasma vitamin B6 levels, and, if necessary, vitamin B6 supplements (pyridoxine (100 mg/day)) will be prescribed
- ALS evaluation procedures: ALSFRS-R, Slow Vital Capacity (SVC), Hand-Held Dynamometry, King's staging system and MiToS, EQ-5D-5L and VAS
- Blood sampling for biomarker: neurofilament light (NFL). Creatinine and creatine kinase will be measured in routine biochemistry lab testing.
- Urine collection for biomarkers: urinary extracellular domain of neurotrophin receptor p75 (Urinary P75ECD) and oxidative stress biomarker 8-hydroxyguanosine (8-OHdG)
- Blood sampling for RNA and serum collection for FBR (if consented)
- Nerve Conduction Study (NCS) (if required)
- Adverse Events monitoring
- Cost questionnaire
- Dispensing study medication
- Compliance check

**Visit 8 Week 72 (Day 504 ±7Days)-End of Trial visit (first 100 patients enrolled)**

The following procedures will be performed:

- Review ongoing concomitant medications
- Complete physical examination
- Neurological examination
- Weight
- Vital signs measured with the subject in a supine/semi-supine position (for at least 5 minutes prior), including blood pressure, pulse rate, pulse oximetry and temperature
- Standard 12-lead ECG (subject should be in a supine/semi-supine position for at least 5 minutes prior to assessment)

- Fasting blood samples for routine clinical labs (clinical chemistry, haematology). See table 2 for lab assessments
- Urine samples for urinalysis
- Urine pregnancy test only in women of childbearing potential
- Plasma vitamin B6 levels, and, if necessary, vitamin B6 supplements (pyridoxine (100 mg/day)) will be prescribed
- ALS evaluation procedures: ALSFRS-R, Slow Vital Capacity (SVC), Hand-Held Dynamometry, ALSAQ-40, Edinburgh Cognitive and Behavioural ALS Screen (ECAS), EQ-5D-5L, VAS, and King's staging system and MiToS
- Blood sampling for biomarker: neurofilament light (NFL). Creatinine and creatine kinase will be measured in routine biochemistry lab testing.
- Urine collection for biomarkers: urinary extracellular domain of neurotrophin receptor p75 (Urinary P75ECD) and oxidative stress biomarker 8-hydroxyguanosine (8-OHdG)
- Blood sampling for RNA and serum collection for FBR (if consented)
- Blood sampling for FAB122 (if early withdrawal)
- Nerve Conduction Study (NCS) (if required)
- Adverse Events monitoring
- Cost questionnaire
- Compliance check

**Table 2: Overview of laboratory assessments**

Haematology	Biochemistry	Urinalysis	Other	Biomarkers
Haematocrit	Bilirubin (direct) and Bilirubin (total)	Blood	Serum $\beta$ -human chorionic gonadotropin ( $\beta$ -hCG)	Urinary P75 ECD
Haemoglobin	Alkaline phosphatase	Glucose	Hepatitis B surface antigen (HBsAg)	Urinary 8-OHdG
RBC	Alanine aminotransferase (ALT)	Protein	Hepatitis C virus antibody (HCV-Ab)	Blood neurofilament light (NFL)
Platelet count	Aspartate aminotransferase (AST)	Specific gravity	HIV antibody (HIV-Ab)	

Haematology	Biochemistry	Urinalysis	Other	Biomarkers
WBC	Bicarbonate	Microscopic exam, if abnormal results are noted	Plasma vitamin B6 levels	
Differential count:	Calcium	Ketone	Cystatin C	
Basophils	Chloride	PH		
Eosinophils	Creatinine	Nitrite		
Lymphocytes	gammaGT (GGT)	Leukocytes		
Monocytes	Fasting Glucose	Bilirubin		
Neutrophils	Potassium	Urobilinogen		
	Sodium			
	Uric Acid			
	Total protein			
	Urea (BUN)			
	eGFR			
	Activated partial thromboplastin time (aPTT)			
	Protrombin Time (PTT)			
	Fibrinogen			
	Lactate dehydrogenase (LDH)			
	Creatinine kinase (CK)			

#### 6.4. Telephonic visits

Seven telephone calls will be performed throughout the study by the study team. These calls will be done in the following time points: Week 8, 16, 20, 28, 32, 40, and 44. The following activities will be performed in each call:

- ALSFRS-R questionnaire
- Adverse Events monitoring
- Review prior and ongoing concomitant medications

#### 6.5. Early Discontinuation/Withdrawal of Participants

Subjects may withdraw consent at any time for any reason or be dropped from the trial at the discretion of the investigator should any untoward effect occur. In addition, a subject may be withdrawn by the investigator or the Sponsor if enrolment into the trial is inappropriate, the trial plan is violated, or for administrative and/or safety reasons.

In this trial, a subject may discontinue from treatment but continue to participate in the regularly scheduled activities, as long as the subject does not withdraw consent. Once a subject has discontinued treatment, he/she may be allowed to start treatment again after consultation with the investigator, if discontinuation of treatment is  $\leq$  2 weeks.

A subject must be discontinued from the trial for any of the following reasons:

- The subject withdraws consent.
- The subject has a medical condition or personal circumstances which, in the opinion of the investigator and/or Sponsor, places the subject at unnecessary risk if participation in the trial is continued.
- The subject reaches the criteria for respiratory insufficiency (tracheostomy or the use of non-invasive ventilation for >20 hours per day for >10 consecutive days),

A subject must be discontinued from study treatment (but should continue to be monitored in the study) for any of the following reasons:

1-The subject becomes pregnant during the study.

2-The subject's investigator considers it is in the best interest of the subject to discontinue including worsening or disease progression if the investigator considers that it is in the patient's best interest the initiation of any standard of care treatment prohibited in the study

3-Serious adverse event considered related to the IMP

4-Severe Neurotoxicity considered related to the IMP

5-Any other severe adverse event considered related to the IMP at the discretion of the investigator.

6-Acute renal failure (creatinine clearance of less than 30 mL/min as calculated by the Cockcroft Gault equation)

7-Severe liver disorder defined as:

- ALT/AST  $\geq$  3xULN and bilirubin  $\geq$  2xULN ( $>35\%$  direct bilirubin)
- ALT/AST  $\geq$  8xULN
- ALT/AST  $\geq$  3xULN and with symptoms believed to be related to liver injury or hypersensitivity.
- ALT/AST  $\geq$  3x baseline ALT/AST and with symptoms believed to be related to liver injury or hypersensitivity.
- ALT/AST  $\geq$  5xULN and ALT/AST  $<$  8xULN that persists more than two weeks

8-Acute lung injury with pyrexia, cough, dyspnoea and chest X-ray abnormality

9-Rhabdomyolysis

10-Disseminated intravascular coagulation (DIC)

11-Hypersensitivity reaction

12- Anaphylactic reaction/shock

13- Thrombocytopenia

14- Neutropenia

15-Introduction of riluzole

16-The subject cannot attend two consecutive study visits and key safety assessment cannot be performed

If a subject discontinues the trial for safety reasons, a PK sample is to be taken (with the time of sampling after last dosing clearly documented) in those sites participating in the PK sub study.

In case a subject withdraws FBR consent, the blood samples taken for FBR will be destroyed (when not analysed yet).

The sponsor reserves the right to terminate the study at any time if continuation of the protocol would present a potential safety risk to the subjects.

Every effort will be made to ensure that patients who do not complete all study requirements return to the site for the End-of-Trial Visit. Patients who withdraw due to an Adverse Event (AE) or Serious Adverse Event (SAE) will be given appropriate care under medical supervision until the symptoms resolve or the patient's condition becomes stable. The End-of-Trial Visit will be performed 7-14 days after withdrawal and the same procedures as Visit 8 will be performed.

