### **11.3.3. Subject Disposition**

Subject disposition (analysis population allocation, entered, discontinued, along with primary reason for discontinuation) will be summarized using frequency and percent for

---

both treatment and follow-up phase. A summary of subjects screened and enrolled will be provided.

A subject is considered to complete the study if he/she completed the 72 week period OR if she/he completed at least 48 week at study completion (i.e. after the last subjects have completed the study up to at least 48 week). Withdrawal from treatment or protocol deviations will not necessarily preclude from recording the respective follow-up information. Efforts will be made to follow all subjects up to 72 or 48 weeks after start of treatment (or to study end if that occurs earlier) and collect data as planned.

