### 11.4. Study Estimand and Handling of Missing Data

To be noted that in this study all efforts will be made to ensure collection of data up to week 48 for all randomized subjects and at least for 100 subjects up to week 72 regardless of treatment withdrawal or protocol deviations.

As per the ICH E9(R1) (*draft addendum on estimands and sensitivity analysis in clinical trials*), the plan for the assessment of the Primary endpoint (PEP) is described here after using the 4 attributes of the estimand:

1. Population: ALS patients fulfilling the selection criteria, as described in section 5 of this protocol
2. Primary endpoint (PEP): Change from baseline in Amyotrophic Lateral Sclerosis Functional Rating Scale – Revised (ALSFRS-R) score after 48 weeks (see sections 3.2.1 and 11.3.4.1)
3. Intercurrent events (IE): The assumptions and expectations on the relevant intercurrent for this study have been based on the publication of a similar trial (Cudkowicz et al., 2013)
4. Accordingly, the following situations have been identified:
  - a. No treatment initiation with the IMP: exclusion from the main analysis with the mFAS population.
  - b. Treatment discontinuation because of adverse events: expected rates  $\approx 3$  (control arm) - 7% (experimental arm).
  - c. Treatment discontinuation because of lack of efficacy: expected rates  $\approx 5$  (control arm) 10% (experimental arm).
  - d. Other treatment related reasons (i.e. due to efficacy or safety issues). To this category will apply other treatment related reasons that those specified in "b" and "c", even that, *a priori*, no potential scenarios are foreseen at the moment of the planning.
  - e. Rescue medication. No clear prevalence rates can be ascertained, but differential higher rates are expected in placebo. This situation is likely to be closely related to IE #c.
  - f. Non treatment-related reasons, others than specified in this list of IE: very low expected rates (i.e.  $\le 1\%$ ). This will also situations like patients moving (not because bad prognosis) to another location or death for completely treatment-unrelated reasons.
  - g. Related death (or death with unknown reasons): it is expected that the rate of death at 52 weeks will be lower than the observed in that trial ( $< 17\%$ ). A non-substantial but lower rate is expected in the experimental arm.

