##### **3.1.2 Modified Intent-to-treat (mITT) Analysis Set**

The mITT analysis set includes all patients who were randomized for this study and received at least 1 dose of investigational product regardless of any protocol deviation. The mITT population will be used for the analysis of efficacy variables, and statistical analysis will be done “as randomized”. The mITT is considered the primary analysis population.

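### Protocol 6.5 allows discretionary withdrawal, most naturally from the trial, for inappropriate enrolment or plan violation, which conflicts with the best-efforts commitment in 11.4 to collect week-48 data despite deviations

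*Protocol*

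**What the plan says.** Protocol 6.5 opens with withdrawal of consent and with patients who may "be dropped from the trial at the discretion of the investigator should any untoward effect occur". It then adds that "a subject may be withdrawn by the investigator or the Sponsor if enrolment into the trial is inappropriate, the trial plan is violated", and goes on to list administrative and safety reasons. The next paragraph is a separate provision: "a subject may discontinue from treatment but continue to participate in the regularly scheduled activities, as long as the subject does not withdraw consent". Later in 6.5 there are two lists, one of reasons that require leaving the trial and one of reasons that require stopping treatment only. The heading of the second list says that monitoring in the study goes on. Section 6.5 ends with an End-of-Trial visit 7-14 days after withdrawal.

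Protocol 11.4 states that "all efforts will be made to ensure collection of data up to week 48 for all randomized subjects", "regardless of treatment withdrawal or protocol deviations". Protocol 11.3.3 is softer: "Withdrawal from treatment or protocol deviations will not necessarily preclude from recording the respective follow-up information". Protocol 11.4 then applies a treatment policy strategy, under which scores observed after an intercurrent event are used, and on that basis expects very little missing data. SAP 3.1.2 defines the primary analysis set as randomised patients who "received at least 1 dose of investigational product regardless of any protocol deviation".

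**The concern.** A deviation is a permitted ground for removal in one section and is expressly not a reason to stop collecting data in another. Suppose a site finds after dosing that a patient missed an entry criterion. It can withdraw that patient under 6.5 and comply fully with the protocol. The patient remains in the mITT, but the later ALSFRS-R scores that the treatment policy estimand needs are not collected. An observed outcome is then replaced by an imputed one, through a decision taken after randomisation that may depend on how the patient is doing.

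Survival time, a key secondary endpoint, is also exposed. SAP 5.6.2 censors patients who discontinue for reasons other than death or respiratory insufficiency. The SAP takes the date of death from a survival follow-up form, but neither document says that this form is completed for a patient removed under this clause.

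**Working it through.** **Does withdrawn mean from the trial?** The clause does not repeat those words, so its scope has to come from context.

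- The sentence before it concerns being dropped from the trial, and the clause continues from it.
- Stopping treatment while staying in follow-up has its own paragraph, limited only by consent.
- The treatment-only list says that monitoring continues. The disputed clause has no such wording.
- SAP 5.3 describes the visit 7-14 days after withdrawal as one for patients who leave the trial early.

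Trial exit is therefore the most natural reading. No section requires ALSFRS-R after such a withdrawal.

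**How would such a patient be analysed?** Removal by site or sponsor for a deviation is not a named intercurrent event in Protocol 11.4 or SAP 5.2. Three rules come near it:

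- Protocol 11.4 gives placebo-reference imputation to missing data among non-treatment-related reasons.
- SAP 5.6.1 limits that imputation to events of unknown cause, whereas here the cause is known.
- SAP 5.2 applies a worst-percentile rule to real loss to follow-up, but defines this by failed attempts at contact.

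**The plan's own sample size (Protocol 11.2: difference 3.0, SD 7.5, 2:1, two-sided 5%, 90% power).**

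- Placebo n = (1 + 1/2) × (1.960 + 1.282)² × 7.5² / 3.0² = 98.5, rounded up to 99. The total is 3 × 99 = 297, against 300 stated.
- At 200:100, SE = 7.5 × √(1/200 + 1/100) = 0.919 and 3.0/0.919 = 3.27. Power is 90.4% (90.2% with the noncentral t).

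The stated figures reproduce. No dropout allowance is given.

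**Size of the effect.** Let w be the share of patients removed before week 48. Under placebo-reference imputation, taking each removed active patient to show no benefit, the loss of effect is w × 3.0.

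- The plan gives no rate for this kind of withdrawal. The nearest is in Protocol 11.4, item f: at most 1% for non-treatment-related reasons not otherwise listed.
- At w = 1%, about 2 of 200 active and 1 of 100 placebo patients are affected. The loss is 0.01 × 3.0 = 0.03 points. Power is 89.9% with the effect diluted to 2.97 and N kept, or 90.1% if the removed patients contribute nothing.
- At w = 5%, an assumption five times the plan's nearest figure, 10 active and 5 placebo patients are affected. The loss is 0.15 points, and power is 87.3% or 88.9% on the same two bases.

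The 0.03 leans high for its rate, because scores observed before removal stay in the repeated-measures data and inform the imputation. If instead one common worst-percentile value were imputed for a share w in both arms, the difference would be (1 − w) × 3.0, which is the same 0.03 at 1%. Unequal removal would add to this by an amount the documents do not allow to be sized.

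**The case against.** The other side has a good case on several points.

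- **The wording is permissive on both sides.** Section 6.5 says that a patient may be withdrawn, 11.4 is a best-efforts statement, and 11.3.3 concedes that follow-up may sometimes stop. A reader might infer that 6.5 breaks a guarantee. The documents give no guarantee.
- **Elsewhere 6.5 keeps deviators in follow-up.** Introduction of riluzole and two consecutive missed visits are both on the treatment-only list. Inappropriate enrolment and plan violation are absent from the list of mandatory trial exits. Protocol section 4 asks for patients who stop treatment to be followed as far as possible.
- **The End-of-Trial visit does not prove that data collection ends.** Footnote 1 of Table 1 requires the same procedures of patients who only stop treatment.
- **The 3 mis-randomised patients in SAP section 6 are not evidence here.** A reader might take them to show that eligibility errors reach the primary analysis. They were never treated, so they are outside the mITT, and the SAP does not say why they were mis-randomised. Eligibility is also rechecked at baseline (Protocol 6.2).
- **The trial is blinded** (Protocol 7.1.2 and 9.8). Removal related to outcome remains possible, but nothing in the documents shows that it would differ between arms.

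These points limit the size and tone of the finding. They do not remove the conflict: the clause gives a discretionary power on the very ground that 11.4 says should not matter, and nothing in 6.5 limits that power to treatment.

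**Conclusion.** The point holds as a conflict between sections that should be resolved, with a probably small effect. Followed as written, 6.5 permits avoidable, discretionary loss of week-48 ALSFRS-R and of survival follow-up in patients who stay in the primary analysis set.

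At the nearest documented rate the cost is at most about 0.03 of 3.0 points. This rests on three assumptions: that such removals fall within item f, that placebo-reference imputation is used, and that removed patients are otherwise typical. Any bias from outcome-related removal is of unknown size and sign. A larger loss, such as 0.15 points, needs a 5% removal rate that nothing in the plan supports.

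**What to change.** Reconcile Protocol 6.5 with 11.3.3 and 11.4. State in 6.5 that inappropriate enrolment or a plan violation found after randomisation and dosing is not by itself a reason to end follow-up. State also that ALSFRS-R, adverse events, concomitant medication and survival continue to be collected to week 48 (week 72 for the first 100 patients) unless consent is withdrawn. Where visits are not possible, use the telephone route already described after the footnotes to Protocol Table 1. SAP 5.1 already treats telephone data as equal in quality to site data.

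This changes data collection only. Safety-based withdrawal, unavoidable administrative withdrawal such as site closure, and all treatment-stopping rules stay as they are. Deleting every administrative withdrawal would go further than the conflict requires.

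The cost is a small amendment to one section and a few extra telephone contacts.
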